### **9.2 Sample size**

The goal of this study is to compare the absolute change in TcPO2 among recently revascularized patients randomized to intervention (ticagrelor) or control (clopidogrel). With 60 patients, 30 per treatment group, this study will have 90% power at an acceptably low type I error rate (0.05) to detect a clinically significant  $8 \pm 8$  mmHg difference in TcPO2, as discussed below.

It is anticipated that most revascularized patients will have a baseline TcPO2 result of approximately 40 mmHg, whereby a 25% change would reflect a final TcPO2 result of 50 mmHg. The standard deviation (SD) for TcPO2 among such a population is estimated to be 16 mmHg based on previously published data (11,19,20). The actual change in TcPO2 that might be induced by either ticagrelor or clopidogrel is unknown. However, based on our hypothesis of improved tissue oxygen tension with ticagrelor, it is anticipated that the ticagrelor group will increase TcPO2 to a greater degree with a SD for the intergroup difference approximately 50% of the baseline SD (16 mmHg). Therefore, we have designed this study to detect an intergroup difference in TcPO2 of  $8 \pm 8$  mmHg assessed at 6 months. Even if clopidogrel induces no change in TcPO2 from baseline, an 8 mmHg increase in the ticagrelor group would represent a 20% improvement over baseline.

Given these assumptions, 26 patients per group will provide sufficient power to detect a large effect size that also reflects a clinically significant change in TcPO2 values. Adjusting for non-adherence and allowing for a 5% rate of crossover from ticagrelor to controls would require 28 patients per group. Attrition rates for this study are anticipated to be low and likely < 5%.

However, given the severity of underlying illness among a population of severely symptomatic PAD, including previously reported mortality rates of 25% at 2 years (21), it seems reasonable to assume our population will have a baseline annual mortality rate of 5-10%. Adjusting the study with 30 patients per group would allow for 7.5% attrition while maintaining power to determine the desired effect.

Finally, our analysis will use 3 repeated measures to assess the TcPO2 endpoint at baseline, 3 months, and 6 months. The Friedman repeated measures ANOVA on ranks will be used to calculate the main effect differences among measurements repeated over time. This technique is particularly suitable if a great deal of variation between samples, especially at low TcPO2, where error variance estimates from standard ANOVA may be large.

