Number of Patients	A sample size of 60 patients (30 per group) provides 90% power to detect an 8±8 mmHg difference in TcPO 2 between groups.

Target Population	Patients with critical limb ischemia either Rutherford Stage IV (without wounds) or Stage V-VI (with concomitant vascular insufficiency wounds) that have been recently revascularized.
Duration of patient participation and duration of the study	The total duration of the study is expected to be 54 months including 48 months for patient recruitment and 6 months for final patient follow-up. Patients will participate in the study for approximately 6 months.
Key Selection Criteria	
INCLUSION CRITERIA
 
 
• Adults age 18-100 years with Rutherford Classification Stage IV through VI PAD with a percutaneous lower extremity arterial angiography with arterial intervention in the past 2 weeks
 
• Willingness to sign informed consent
 
• Ability to return for follow-up visits
 
• A female patient of childbearing potential who is sexually active must agree to use adequate contraception from screening until 30 days after receiving the last dose of study drug.
 
 
EXCLUSION CRITERIA
 
 
• Intolerance to thienopyridines
 
• Hypersensitivity to ticagrelor or any component of the product
 
• Concomitant use of oral anticoagulation with vitamin K antagonist, factor Xa inhibitor, or direct thrombin inhibitor
 
• History of intracranial hemorrhage
 
• History of severe hepatic impairment defined by baseline transaminase greater than or equal to 3x ULN or any elevation in bilirubin
 
• Active bleeding
 
• Allergy to aspirin
 
• Baseline TcPO2 < 10 mmHg post angiography
 
• Resting pre-procedure heart rate < 50 beats-per-minute without a permanent pacemaker and not on an atrioventricular nodal blocking agent
 
• Severe COPD on home oxygen therapy
 
• Patients on strong CYP3A inhibitors and/or CYP3A inducers that cannot be stopped for the course of the study.
 

Study Visit Schedule and Assessments	Visits will occur at screening (baseline) post angiography, and at 3 and 6 months.
Test Product, Dose, and Mode of Administration	Patients will be randomized to either ticagrelor 90 mg by mouth twice daily or clopidogrel 75 mg by mouth daily.
Concomitant Medications	Aspirin 81 mg by mouth every day

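### Does the 90% power claim fail because the planning SD of 8 mmHg is half the only sourced SD of 16 mmHg?

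*Combined protocol and SAP*

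**What the plan says.** The Synopsis (Number of Patients) states: "A sample size of 60 patients (30 per group) provides 90% power to detect an 8±8 mmHg difference". Section 9.2 repeats the figure at a type I error of 0.05 and explains it in four steps.

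- **Sourced spread.** The SD of TcPO2 "among such a population is estimated to be 16 mmHg based on previously published data (11,19,20").
- **Effect.** The change "that might be induced by either ticagrelor or clopidogrel is unknown". Even so, "based on our hypothesis of improved tissue oxygen tension with ticagrelor, it is anticipated that the ticagrelor group will increase" TcPO2 by more than the clopidogrel group.
- **Planning SD.** The same sentence adds the figure of 8, "with a SD for the intergroup difference approximately 50% of the baseline SD (16 mmHg").
- **Sample size.** On the assumptions just listed, "26 patients per group will provide sufficient power to detect a large effect size". Next, "allowing for a 5% rate of crossover from ticagrelor to controls would require 28 patients per group". Finally: "Adjusting the study with 30 patients per group would allow for 7.5% attrition while maintaining power to determine the desired effect".

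Section 9.1 makes the primary analysis an MMRM of absolute change in TcPO2, adjusted for the post-revascularization baseline, with two-sided testing at 0.05.

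**The concern.** The required sample size grows with the square of the SD, so halving the SD divides it by four. The only SD with a citation is 16 mmHg. The step to 8 mmHg comes in a sentence whose stated basis is a hypothesis about the mean response to ticagrelor, and a larger mean response does not imply a smaller spread. The label is also loose: an SD for the intergroup difference could mean the SD of each patient's change or the SD of the difference between two patients' changes. No power is shown at any other SD, and neither the test nor the target power behind 26 per group is named.

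If the true SD were well above 8 mmHg, the trial would have much less than 90% power, and a null result might be read as stronger evidence against an 8 mmHg effect than it is.

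**Working it through.** **Inputs.** Difference 8 mmHg, SD 8 mmHg, 26 then 28 then 30 per group, 5% crossover, 7.5% attrition and sourced SD 16 mmHg (all Section 9.2); two-sided 0.05 and baseline adjustment (Section 9.1); 1:1 allocation (Section 4.2).

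**1. The plan's own figure.** Normal formula: n per group = 2(z₀.₉₇₅ + z_power)² × (SD/difference)².

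- 90% power: 2 × (1.960 + 1.282)² × (8/8)² = 21.0, so 22; by the t-test, 23.
- 95% power: 2 × (1.960 + 1.645)² × (8/8)² = 25.99, so 26. This matches the plan's 26, but the plan does not say it is the route used.
- t-test power at SD 8: 94.2% with 26 per group and 96.8% with 30.

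So 90% is a floor at SD 8 and not an overstatement.

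**2. After the plan's losses.** Crossover dilutes the difference to 8 × 0.95 = 7.6 mmHg. Attrition leaves 30 × 0.925 = 27.75 per group. The noncentrality is 7.6 × √(27.75/2)/8 = 3.54, which gives 93.5% power. With a worst-case rank-test efficiency of 0.864 (an assumption, relevant to the rank-based fallback in Section 9.1), 30 per group after losses still gives 89.6%.

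**3. The two readings of the label.** If 8 were the SD of the difference between two patients' changes, the per-patient SD would be 8/√2 = 5.66 and 12 per group would give 90%. If 8 is the per-patient SD, 23 are needed. The plan's 26 fits the second reading, which is the less favourable one and is used here.

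**4. Is 16 the right comparator?** It is an SD of values. Suppose the SD is 16 at both visits (an assumption) and let r be the correlation between baseline and month 6.

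- SD of raw change = 16√(2(1 − r)). This equals 8 when r = 0.875.
- Baseline-adjusted SD = 16√(1 − r²). This equals 8 when r = √(1 − (8/16)²) = 0.866.

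A baseline-adjusted SD of 16 would need r = 0, meaning that a patient's baseline reading says nothing about the month-6 reading.

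**5. Sensitivity.** 30 per group, difference 8 mmHg, t-test. SDs above 8 are assumptions.

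| SD of baseline-adjusted change | Implied r | Power, no losses | Power after losses |
|---|---|---|---|
| 8 | 0.87 | 97% | 93.5% |
| 8.6 | 0.84 | 94% | 90% |
| 10 | 0.78 | 86% | 79% |
| 12 | 0.66 | 72% | 64% |

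The largest SD that keeps 90% is 9.4 mmHg without losses (59% of 16) and 8.6 mmHg with them (54% of 16).

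**The case for a change.** The best case for a change is that the margin is thin and the cure is cheap. After losses, the planning SD can rise from 50% to only about 54% of 16 mmHg before power drops below 90%, and to about 62% before it drops below 80%. Section 9.2 gives no correlation or SD of change by which to judge whether it will stay there. It also allows for large variation between samples. A few sentences would name the SD, give its basis and show the sensitivity.

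Part of this stands. The SD of 8 is unsourced and loosely labelled, no sensitivity is shown, and the route to 26 per group is not given. Two of the references cited for the 16 mmHg have titles about variability or reproducibility, but the text does not use them to support the 50%.

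Two stronger forms do not stand. First, the power is not presented as unconditional. Both statements print 8 ± 8 mmHg, and Section 9.2 ties the 26 per group to the assumptions it has just listed. Second, the power at SD 16 (48%, or 41% after losses) is not an estimate of the trial's true power. In the baseline-adjusted analysis it is the zero-correlation extreme. Nor must the sentence be read as deriving the SD from the hypothesis: the hypothesis supports the larger rise, and the SD clause can be read as a separate design assumption.

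**Conclusion.** The concern does not call for a change. The plan discloses the SD on which its power depends, and at that SD the design delivers more than it claims: 97% with all patients analysed and 93.5% after the stated losses, against 90%. This rests on reading 8 mmHg as the per-patient SD of the 6-month change and on a two-sample t-test as a stand-in for the baseline-adjusted MMRM.

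What remains is missing detail about a planning assumption. Power would fall to 79% at SD 10 and 64% at SD 12 after losses, but the documents hold no evidence that the SD is that large, just as they hold none that it is 8. Writing this down would leave the 60 patients, the analysis, the conduct and the results of this pilot unchanged.

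The risk of over-reading a null result is also limited. The MMRM estimates the between-group difference in LS means, and its precision will reflect the observed spread rather than the planned one. That safeguard is weaker if the rank-based fallback is used, because group differences are then shown only as F statistics. The medians and interquartile ranges would still show how variable the data were.

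### Do the figures of 26, 28 and 30 per group in section 9.2 contradict each other or the stated 90% power?

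*Combined protocol and SAP*

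**What the plan says.** The Study Synopsis gives the headline: "A sample size of 60 patients (30 per group) provides 90% power to detect an 8±8 mmHg difference". Section 9.2 repeats it: "With 60 patients, 30 per treatment group, this study will have 90% power at an acceptably low type I error rate (0.05". Section 9.1 makes the tests two-sided.

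Section 9.2 then builds up to 30 per group:

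- Variability: the SD of TcPO2 "is estimated to be 16 mmHg based on previously published data (11,19,20". Ticagrelor is expected to raise TcPO2 "to a greater degree with a SD for the intergroup difference approximately 50% of the baseline SD (16 mmHg", which gives the 8±8 mmHg design value.
- Starting size: "Given these assumptions, 26 patients per group will provide sufficient power to detect a large effect size". No percentage is attached to 26.
- Crossover: "allowing for a 5% rate of crossover from ticagrelor to controls would require 28 patients per group".
- Attrition: first put at probably under 5%, then reconsidered in the light of "mortality rates of 25% at 2 years (21), it seems reasonable to assume our population will have a baseline annual mortality rate of 5-10" per cent. The step ends: "Adjusting the study with 30 patients per group would allow for 7.5% attrition while maintaining power to determine the desired effect".

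**The concern.** Someone who tries to rebuild the section meets four obstacles.

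1. At 8±8 mmHg and two-sided 0.05, the usual formula for 90% power gives 22 or 23 per group, not 26.
2. 30 per group less 7.5% leaves 27.75, below the 28 that the preceding step requires, so the claim that power is maintained seems to fail.
3. The SD of 8 is described as that of an intergroup difference. A two-group formula needs the within-arm, per-patient SD of the quantity analysed. The cited sources support 16, not its halving, and no baseline-to-6-month correlation is given.
4. 25% mortality at 2 years sits beside an assumed 5-10% a year, which is lower.

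If these were real contradictions, the stated power could be wrong, and a null result in a 60-patient trial would be hard to interpret.

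**Working it through.** **Inputs.** From sections 9.1 and 9.2 and the Synopsis: two-sided alpha 0.05, difference 8 mmHg, SD 8 mmHg, 1:1 allocation, 5% crossover, 7.5% attrition, and 26, 28 and 30 per group. Assumption: 8 is the per-arm SD of the analysed quantity.

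**Starting size.** The normal formula is n = 2(z_alpha + z_beta)²(SD/difference)².

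- 90% power: 2(1.960 + 1.282)² = 21.01, so 22. By t-test, 22 gives 89.97%, so 23.
- 95% power: 2(1.960 + 1.645)² = 25.99, so 26.

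The plan's 26 therefore matches 95% power by the normal formula (94.2% by t-test). The text does not say that this was the target.

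**Headline power by t-test at SD 8.**

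| Per group | Difference | Power |
|---|---|---|
| 26 | 8 | 94.2% |
| 28 | 8 | 95.7% |
| 30 | 8 | 96.8% |
| 30 × 0.925 = 27.75 | 8 | 95.5% |
| 27.75 | 8 × 0.95 = 7.6 (5% dilution) | 93.5% |

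Every row exceeds 90%.

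**Loss steps.**

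- Crossover as n/(1 − c): 26/0.95 = 27.37, so 28. This reproduces the plan.
- Both losses, rounded once at the end: 26/0.95/0.925 = 29.59, so 30. This also reproduces the plan.
- In reverse: 30 × 0.925 × 0.95 = 26.36, which is not below 26.

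The apparent shortfall arises only when 27.37 is first rounded to 28 and the attrition factor is then applied to the rounded figure: 28/0.925 = 30.27. The gap of 28 − 27.75 is a quarter of a patient per group.

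**Mortality.** At a constant rate, 25% at 2 years is 1 − 0.75^0.5 = 13.4% a year, or 1 − 0.75^0.25 = 6.9% at 6 months. A rate of 5-10% a year gives 1 − 0.95^0.5 = 2.5% to 1 − 0.90^0.5 = 5.1% at 6 months. Even the higher figure, 6.9%, is within the 7.5% allowed.

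**Sensitivity to the SD.** With SD 16 at both visits (an assumption), a change-score SD of 8 requires 16√(2(1 − r)) = 8, so r = 0.875. A baseline-adjusted SD of 8 requires 16√(1 − r²) = 8, so r = 0.866. Power at 30 per group, without losses, for other assumed correlations:

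| Correlation | Change score | Baseline-adjusted |
|---|---|---|
| 0.8 | 85% | 89% |
| 0.7 | 69% | 76% |
| 0.5 | 48% | 59% |

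Power falls below 90% once the SD exceeds 9.4 mmHg with no losses, 9.0 with attrition, or 8.6 with attrition and dilution.

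If 8 is instead the SD of a difference between two patients, the per-arm SD is 8/√2 = 5.66 and 90% power needs 11 or 12 per group. That reading leaves the trial with more power, not less.

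**The case for a change.** The strongest case for a change is the SD. Section 9.2 admits that the effect of either drug on TcPO2 is unknown, yet the planning SD is half of a sourced value with nothing behind the halving. A correlation of about 0.87 over six months is high, and the table shows how quickly power falls below it. This stands as a criticism of how the assumption is documented. It does not show that 8 is wrong, since the documents contain no estimate of the correlation.

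A second argument is that crossover is better treated as dilution of the effect, so the inflation factor should be squared: 26/0.95² = 28.8, and 28.8/0.925 = 31.1, above 30. The method is legitimate, but the plan's 28 matches the simple factor; the squared one would give 29. At the stated SD the choice does not matter, because the diluted effect with 27.75 per group still has 93.5% power. To get below 90% one must take 26 as the exact 90% figure, which by t-test needs an SD of 8.73. Power after losses is then 89.0%, but that SD is not in the plan and conflicts with 8±8.

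It is also true that the power behind 26 is unnamed and that the mortality sentence passes from a higher rate to a lower one without a reason. Both are gaps in explanation. The first errs on the safe side, and the attrition allowance covers the second as far as deaths alone are concerned. Deaths and other dropouts together could exceed 7.5%, but 28 of 30 or 26 of 30 remaining still gives 95.7% or 94.2% at SD 8 without dilution.

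**Conclusion.** The concern does not call for a change. The claim on which the trial rests, 90% power with 30 per group for 8±8 mmHg, holds with margin if 8 is the per-arm SD: 96.8% at full enrolment and 93.5% after 7.5% attrition and a 5% diluted effect. The 26, 28, 30 sequence follows from the plan's own loss rates with ordinary rounding.

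Section 9.2 does leave out the test and target power behind 26, and the basis for taking the SD as 8. A statistician can recover the first from the figures. The second is an openly stated planning assumption in a pilot trial. A sentence on its origin would help a reader, but would alter neither the 60 patients, the endpoint nor the MMRM. That model estimates its variance from the trial data, so an optimistic planning SD would cost precision without biasing the treatment comparison. The documents plan no sample-size re-estimation that would use the value of 8.

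The conclusion rests on reading 8 mmHg as the per-arm SD of the change or of the baseline-adjusted residual. If the true SD is above about 9.4 mmHg (8.6 after the plan's losses), power is below 90%. That is a risk of the assumption, not an inconsistency in the calculation.

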## **10 Study Committees**

The following committees will be responsible for the management of the study and the monitoring of the safety of the study patients.

### **10.1 Executive Steering Committee**

The Executive Steering Committee (ESC) will have scientific responsibility for the study. They will review study conduct and progress, consider recommendations from the Medical Monitor and resolve any other study related issues.

### **10.2 Safety Monitoring Board**

An independent Medical Monitor will be appointed to monitor the study by reviewing the case report forms, SAE and AE forms at specified intervals throughout the study and will be responsible for the oversight of safety.

## **11 Data Handling and Record Keeping**

### **11.1 Data Collection**

Data will be collected by the Nurse or Site Coordinator or designee. Data sources include patient reports and available medical records, including those from electronic medical record. Values for preoperative variables will be selected nearest to the date of the revascularization procedure, but used only if they were obtained within 30 days of the procedure.

C5Research Data Management will create a Case Report Form to document the agreed upon variables to be captured in the REDCap database.

### **11.2 REDCap Database:**

Study data will be collected and managed by the site using REDCap (Research Electronic Data Capture). REDCap is a secure, web application designed to support data capture for research studies, providing user-friendly web-based case report forms, real-time data entry validation (e.g. for data types and range checks), audit trails and a de-identified data export mechanism to common statistical packages (SPSS, SAS, Stata, R/S-Plus). The system was developed by a multi-institutional consortium which includes Cleveland Clinic and was initiated at Vanderbilt University. The database is hosted at the Cleveland Clinic Datacenter. The system is protected behind a login and Secure Sockets Layer (SSL) encryption. There is an audit trail tracking all logins and activities in the database. Data collection is customized for each study or clinical study based on a study-specific data dictionary defined by the research team with guidance from the REDCap administrator in Quantitative Health Sciences at the Cleveland Clinic.

### **11.3 REDCap Completion Guidelines:**

Cleveland Clinic Data Management (DM) will create a REDCap Completion Guidelines document to assist the site in data entry.

### **11.4 Retention of Records**

Investigator files containing study related documents will be retained according to the agreed timeframe outlined in the contractual agreement and at least for a minimum of two (2) years after a marketing application is approved for the drug; or 2 years after investigational use is discontinued and FDA has been notified in accordance with the applicable regulations.

Records shall be accessible for inspection by authorized representatives of the Sponsor, or the FDA. Records may be discarded upon written notification by the Sponsor. To avoid error, the Principal Investigator should contact C5Research / AstraZeneca, before the destruction of any records and reports pertaining to the study to ensure they no longer need to be retained. In addition, the Sponsor should be contacted if the Principal Investigator plans to leave the investigational site so that appropriate arrangements for file custodianship can be made.

## **12 Study Monitoring, Auditing, and Inspecting**

C5Research is responsible for monitoring the safety and effectiveness of this study.

The study will be monitored according to the Monitoring Plan, per the applicable C5Research Standard Operating Procedures for clinical monitoring and in compliance with Title 21 CFR Part 312.

### **13 Ethical Considerations**

This study will be performed in accordance with the protocol, International Conference on Harmonization Good Clinical Practice guidelines and the Cleveland Clinic IRB.

The Investigator has the ethical and legal responsibility to ensure that each patient is given a full explanation of the study. Written informed consent will be obtained from all patients before any study-specific procedures are performed.

The Cleveland Clinic IRB must review and approve the protocol and informed consent form before the study can begin.

### **14 Publication**

The study investigators will present and publish the results of the study.

# Appendix A

**CLOPIDOGREL BISULFATE- clopidogrel bisulfate tablet, film coated**  
Mylan Institutional Inc.

-----

## HIGHLIGHTS OF PRESCRIBING INFORMATION

These highlights do not include all the information needed to use clopidogrel tablets safely and effectively. See full prescribing information for clopidogrel tablets.

Clopidogrel Tablets, USP  
Initial U.S. Approval: 1997

